## Appendix B. European LeukemiaNet (ELN) Response Criteria in Acute Myeloid Leukemia (2017)

Category	Definition	Comment
Response		
• CR without minimal residual disease (CR MRD- )	If studied pretreatment, CR with negativity for a genetic marker by RT-qPCR, or CR with negativity by MFC	Sensitivities vary by marker tested, and by method used; therefore, test used and sensitivity of the assay should be reported; analyses should be done in experienced laboratories (centralized diagnostics)
• Complete remission (CR)	Bone marrow blasts < 5%; absence of circulating blasts and blasts with Auer rods; absence of extramedullary disease; ANC $\geq 1.0 \times 10^9/L$ (1000/ $\mu$ L); platelet count $\geq 100 \times 10^9/L$ (100 000/ $\mu$ L)	MRD + or unknown
• CR with incomplete hematologic recovery (CRI)	All CR criteria except for residual neutropenia ( $< 1.0 \times 10^9/L$ [1000/ $\mu$ L]) or thrombocytopenia ( $< 100 \times 10^9/L$ [100 000/ $\mu$ L])	
• Morphologic leukemia-free state (MLFS)	Bone marrow blasts < 5%; absence of blasts with Auer rods; absence of extramedullary disease; no hematologic recovery required	Marrow should not merely be "aplastic"; at least 200 cells should be enumerated or cellularity should be at least 10%
• Partial remission (PR)	All hematologic criteria of CR; decrease of bone marrow blast percentage to 5% to 25%; and decrease of pretreatment bone marrow blast percentage by at least 50%	Especially important in the context of phase 1-2 clinical trials
Treatment failure		
• Primary refractory disease	No CR or CRI after 2 courses of intensive induction treatment; excluding subjects with death in aplasia or death due to indeterminate cause	Regimens containing higher doses of cytarabine are generally considered as the best option for subjects not responding to a first cycle of 7+3; the likelihood of responding to such regimens is lower after failure of a first
• Death in aplasia	Deaths occurring $\geq 7$ d following completion of initial treatment while cytopenic; with an aplastic or hypoplastic bone marrow obtained within 7 d of death, without evidence of persistent leukemia	
• Death from indeterminate cause	Deaths occurring before completion of therapy, or $< 7$ d following its completion; or deaths occurring $\geq 7$ d following completion of initial therapy with no blasts in the blood, but no bone marrow examination available	

Footnotes defined on next page

Page 1 of 2

Category	Definition	Comment
Response criteria for clinical trials only		
• Stable disease	Absence of CR MRD -, CR, CRi, PR, MLFS; and criteria for PD not met	Period of stable disease should last at least 3 mo
Relapse		
• Progressive disease (PD) a,b	Evidence for an increase in bone marrow blast percentage and/or increase of absolute blast counts in the blood: 
 
• > 50% increase in marrow blasts over baseline (a minimum 15% point increase is required in cases with < 30% blasts at baseline; or persistent marrow blast percentage of > 70% over at least 3 mo; without at least a 100% improvement in ANC to an absolute level (<math>> 0.5 \times 10^9/L [500/\mu L]</math>), and/or platelet count to <math>> 50 \times 10^9/L [50000/\mu L]</math> nontransfused); or
 
• > 50% increase in peripheral blasts (WBC <math>\times</math> % blasts) to <math>> 25 \times 10^9/L (> 25000/\mu L)</math> (in the absence of differentiation syndrome)b; or
 
• New extramedullary disease
 
	Category mainly applies for older subject given low intensity or single-agent “targeted therapies” in clinical trials. In general, at least 2 cycles of a novel agent should be administered. Some protocols may require blast increase in 2 consecutive marrow assessments at least 4 wk apart; the date of progression should then be defined as of the first observation date. Some protocols may allow transient addition of hydroxyurea to lower blast counts. Hydroxyurea is unapproved for AML in Japan. “Progressive disease” is usually accompanied by a decline in ANC and platelets and increased transfusion requirement and decline in performance status or increase in symptoms.
• Hematologic relapse (after CR MRD -, CR, CRi)	Bone marrow blasts $\geq 5\%$ ; or reappearance of blasts in the blood; or development of extramedullary disease	
• Molecular relapse (after CR MRD -)	If studied pretreatment, reoccurrence of MRD as assessed by RT-qPCR or by MFC	Test applied, sensitivity of the assay, and cutoff values used must be reported; analyses should be done in experienced laboratories (centralized diagnostics)

Page 2 of 2

ANC = absolute neutrophil count; d = day(s); IDH = isocitrate dehydrogenase; MLFS = morphologic leukemia-free state; mo = month(s); WBC = white blood cell; wk = week(s)

a The authors acknowledge that this new provisional category is arbitrarily defined; the category aims at harmonizing the various definitions used in different clinical trials.

b Certain targeted therapies, for example, those inhibiting mutant IDH proteins, may cause a differentiation syndrome, that is, a transient increase in the percentage of bone marrow blasts and an absolute increase in blood blasts; in the setting of therapy with such compounds, an increase in blasts may not necessarily indicate PD.

### Appendix C. Code Fragments

The ORR and its 95% CI can be calculated in SAS using PROC FREQ. The sample code is provided below, where RESP is the status of response (eg., 1=responder, 2=non-responder). The CI using the exact method can be found in the OUT data labeled as 'Exact Conf Limits'.

```
proc freq data=TEST;
tables RESP / binomial alpha=0.05;
ods output Binomial=OUT;
run;
```

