4.3.3 Justification of the Monotherapy Recommended Phase 2 Dose (RP2D)

In the current study, **Part 1** and **Part 2** were initially designed to investigate tapotoclax as monotherapy and combinational therapy in subjects with multiple myeloma (MM). As of December 2019, 48 subjects were enrolled in **Part 1** where clinical responses were observed at dose levels $> 240 \text{ mg/m}^2$. At that time, tapotoclax-associated elevations of troponin were observed at dose levels of 360 mg/m^2 and 480 mg/m^2 . Consequently, to avoid the potential for troponin elevations, only doses less than equal to 240 mg/m^2 are currently under investigation. Additionally, monotherapy efficacy of tapotoclax in AML has been limited, with an overall response rate (ORR = CR + incomplete hematologic recovery [CRI]) of 9.4% (3 out of 32 subjects) in monotherapy **Parts 3a, 3b, and 3c** (all responses were CRI). In contrast, increased antileukemic activity has been observed in combination with azacitidine. Consequently, combination therapy has been prioritized in the current study (**Parts 4 and 5**) to optimize the clinical benefit to subjects, and monotherapy investigations were completed to support the combination therapy studies.

As of November 2022, in AML subjects, 2 out of 17 subjects in **Part 3a** (ORR = 11.8%), 1 out of 11 subjects in **Part 3b** (ORR = 9.1%), 0 out of 4 subjects in **Part 3c** (ORR = 0%), and 3 out of 21 subjects in **Part 4** (ORR = 14.3%) have achieved the best overall response of CR or CRI. With the 21 AML subjects who received combination tapotoclax plus azacitidine in **Part 4**, 12 subjects had at least 1 evaluable disease response; 2 subject (9.6%) had CR; 1 subject (4.8%) had CRI; 8 subjects (38.1%) had stable disease (SD); 1 subject (4.8%) had PD (9 subjects [42.9%] did not have an evaluable disease response) (see [Table 2-1](#) for details). Three out of 21 subjects (14.3%) achieved CRI or better in all cohorts in **Part 4**, and 2 out of 6 subjects (33%) achieved CR in tapotoclax 240 mg/m^2 QW plus azacitidine cohort, demonstrating a better response at the 240 mg/m^2 dose compared with lower doses when administered in combination with azacitidine.

Preliminary PK/PD modeling for tapotoclax (monotherapy or in combination with azacitidine) to date have shown subtherapeutic exposures with regard to the estimated minimum efficacious exposures for tapotoclax at doses below 240 mg/m².

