### 9.5.2 Analyses of Secondary Efficacy Endpoint(s)/Estimand(s)

Table 3. Efficacy Endpoint Summary

Endpoint	Statistical Analysis Methods
ORR	The proportion of subjects with response (PR or better) with corresponding 2-sided exact 95% CI will be calculated using the Clopper-Pearson method ( Clopper and Pearson, 1934 ) for the Full Analysis Set. Refer Appendix C for code fragment.
DOR, PFS (for MM) and EFS (for AML)	Kaplan-Meier estimates and Kaplan-Meier curve will be provided for the Full Analysis Set.
TTR	Descriptive statistics will be provided for subjects with response.

For time to event endpoints (including DOR, TTR, EFS and PFS), summary table or figure may not be generated if the number of events is less than 10. The individual subject-level data will be provided.

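### The sample ORR code in SAP Appendix C is correct only when a cohort has at least one responder; for a cohort with none it reports the non-responder rate

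*SAP*

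**What the plan says.** SAP Section 9.5.2, Table 3, defines the ORR analysis on the Full Analysis Set: "The proportion of subjects with response (PR or better) with corresponding 2-sided exact 95% CI will be calculated using the Clopper-Pearson method". It then refers to Appendix C for the code.

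Appendix C introduces the fragment with "The sample code is provided below" and describes the input variable: "where RESP is the status of response (eg., 1=responder, 2=non-responder". The procedure call is "proc freq data=TEST", followed by "tables RESP / binomial alpha=0.05", with the binomial output sent to a data set called OUT. The reader is told to take the exact limits from OUT. There is no LEVEL= option, no WEIGHT statement with ZEROS, and no BY statement.

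Three other places in the SAP determine how the fragment would be used:

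- Section 9.1 summarizes efficacy by dose level within each indication.
- Section 5 (Overall Response Rate) counts every subject without PR or better as a non-responder. For AML, PR or better includes MLFS.
- Section 10 lists the analyses dropped after early termination. ORR is not among them.

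**The concern.** A one-way table of RESP contains only the values that occur. In a cohort with at least one responder, the first value is 1 and the reported proportion is the response rate. In a cohort with none, the Section 5 rule sets every record to 2. The first and only level is then the non-responder, and both the proportion and the exact limits in OUT describe non-responders.

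Dose cohorts in this trial are small, so cohorts with no responder are to be expected. With PFS, EFS and TTR dropped, ORR is one of the few efficacy results still planned. If the error went unnoticed, a dose with no activity would be tabulated as one where every subject responded.

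**Working it through.** **Inputs**

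- Method: 2-sided exact 95%, Clopper-Pearson (SAP Table 3), so 0.025 per tail.
- Coding and code: Appendix C, as described above.
- Cohorts with no responder: Protocol Table 2-1 has two N=5 columns with no CR, CRi, MLFS or PR. They are 60 mg/m² QW plus azacitidine and 120 mg/m² QW monotherapy.
- Assumption from outside the documents: with no LEVEL= option, PROC FREQ reports the first level present in the data. This default was emulated; it was not run in SAS.

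**The plan's own figures**

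The documents give no ORR confidence interval to reproduce. The point estimates in Protocol Section 4.3.3 do reproduce: 3/32 = 9.4%, 2/17 = 11.8%, 1/11 = 9.1%, 3/21 = 14.3%.

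**Formulas**

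For x responders of n, the lower limit is the 0.025 quantile of Beta(x, n−x+1) and the upper limit is the 0.975 quantile of Beta(x+1, n−x). At the ends these reduce to:

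- x = 0: interval from 0 to 1 − 0.025^(1/n)
- x = n: interval from 0.025^(1/n) to 1

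**A cohort with no responder, n = 5**

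- 0.025^(1/5) = 0.478.
- Correct result (x = 0): 0%, interval 0% to 1 − 0.478 = 52.2%.
- Fragment as written (only level 2 present, counted as 5 of 5): 100%, interval 47.8% to 100%.

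**Cohorts with and without responders**

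| Responders/n | Correct ORR (95% CI) | Fragment, run per cohort |
|---|---|---|
| 0/5 | 0% (0%, 52.2%) | 100% (47.8%, 100%) |
| 1/5 | 20.0% (0.5%, 71.6%) | the same |
| 2/6 | 33.3% (4.3%, 77.7%) | the same |

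The fault is confined to cohorts with no responder. There the point estimate is off by 100 percentage points and the interval is the mirror image of the right one.

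**Part 3c**

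Protocol Section 4.3.3 gives 0 of 4, but on CR plus CRi. The SAP endpoint also counts PR and MLFS, which that section does not report for Part 3c. If Part 3c is also 0/4 on the SAP endpoint, then 0.025^(1/4) = 0.398. The correct result would be 0% (0%, 60.2%) and the fragment would give 100% (39.8%, 100%). The documents do not establish that case.

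**The case against.** The strongest reply is that the specified analysis is right and only an illustration is incomplete. Table 3 and Section 5 together require 0% (0%, 52.2%) for a 0/5 cohort, so a 100% output would itself depart from the SAP. The fragment is labelled as sample code, its coding is given as an example, its data set is a placeholder, and it has no BY statement. On a pooled set with any responder it is correct. SAP Section 8.7 provides for output verification, validation under an SOP, and standard macros where available. A 100% ORR would also clash with the subject-level best overall response.

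Most of this stands, and it limits how far the point can be taken. It does not make the fragment correct. Table 3 names it as the reference, results are required by dose level, nothing warns of the empty cell, and a validator working from the same fragment would repeat the error.

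The supporting data have limits too. Table 2-1 is an interim snapshot with some subjects still active. One of the two columns with no responder is headed Part 3b although it is a combination with azacitidine. The Part 3b monotherapy columns sum to 5 + 5 + 4 = 14, against 11 enrolled in Protocol Section 4.2. Two is therefore an indicative count of such cohorts and not a final one.

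A reader might also infer from the myeloma responses reported above 240 mg/m² that the low-dose myeloma cohorts had no responders. The documents do not say so.

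**Conclusion.** The reference code is wrong for any dose cohort without a responder and right for all others. For 0/5 the output is 100% (47.8%, 100%) where 0% (0%, 52.2%) is required. This rests on two assumptions: that PROC FREQ's default is the first level present, and that the fragment is run separately by dose level without other adaptation. Running it on five records all coded 2 would settle the first.

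Two stronger readings are tempting and are not supported. One is that inactive doses have been, or will be, reported as 100% ORR. No production program or table is visible, and Section 8.7 may catch the error. The other is that the dose-response picture would be reversed. Cohorts with any responder keep their correct values, so only the cohorts without one would be misplaced.

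This should be fixed, but it does not invalidate the planned ORR analysis.

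**What to change.** Replace the Appendix C fragment with code that keeps the empty cell and names the responder level. Supply one count row per RESP level for each part, schedule and dose, including rows with a count of zero. Then use `weight COUNT / zeros; tables RESP / binomial(level='1') alpha=0.05;` with BY processing on part, schedule and dose.

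Naming the level alone is not enough, because level 1 is absent from the data in exactly the cohorts that fail. Naming it in addition to the zero row stops the result from depending on a coding that the SAP gives only as an example. Computing the Clopper-Pearson limits directly from x and n would serve equally well.

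Add a 0-of-n case to the validation, with 0/5 = 0% (0%, 52.2%) as the expected result. If ORR tables already exist, check each cohort without a responder against subject-level best response.

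The cost is one code fragment and one test case. No data, endpoint or definition changes.
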